1.2.2 Cetuximab

Cetuximab (Erbitux®) is a recombinant, human/mouse chimeric monoclonal antibody that binds specifically to the extracellular domain of the human epidermal growth factor receptor (EGFR). Cetuximab is composed of the Fv regions of a murine anti-EGFR antibody with human IgG1 heavy and kappa light chain constant regions and has an approximate molecular weight of 152 kDa. Cetuximab is produced in mammalian (murine myeloma) cell culture.

Cetuximab is a sterile, clear, colorless liquid of pH 7.0 to 7.4, which may contain a small amount of easily visible, white, amorphous cetuximab particulates. Cetuximab is supplied at a concentration of 2 mg/mL in either 100 mg (50 mL) or 200 mg (100 mL), single-use vials. Cetuximab is formulated in a solution with no preservatives, which contains 8.48 mg/mL sodium chloride, 1.88 mg/mL sodium phosphate dibasic heptahydrate, 0.41 mg/mL sodium phosphate monobasic monohydrate, and Water for Injection, USP.

The epidermal growth factor receptor (EGFR, HER1, c-ErbB-1) is a transmembrane glycoprotein that is a member of a subfamily of type I receptor tyrosine kinases including EGFR, HER2, HER3, and HER4. The EGFR is constitutively expressed in many normal epithelial tissues, including the skin and hair follicle. Expression of EGFR is also detected in many human cancers including those of the head and neck, colon, and rectum.

Cetuximab binds specifically to the EGFR on both normal and tumor cells, and competitively inhibits the binding of epidermal growth factor (EGF) and other ligands, such as transforming growth factor-alpha. *In vitro* assays and *in vivo* animal studies have shown that binding of cetuximab to the EGFR blocks phosphorylation and activation of receptor-associated kinases, resulting in inhibition of cell growth, induction of apoptosis, and decreased matrix metalloproteinase and vascular endothelial growth factor production. Signal transduction through the EGFR results in activation of wild-type *Ras* proteins, but in cells with activating *Ras* somatic mutations, the resulting mutant *Ras* proteins are continuously active regardless of EGFR regulation.

In vitro, cetuximab can mediate antibody-dependent cellular cytotoxicity (ADCC) against certain human tumor types. *In vitro* assays and *in vivo* animal studies have shown that cetuximab inhibits the growth and survival of tumor cells that express the EGFR. No anti-tumor effects of cetuximab were observed in human tumor xenografts lacking EGFR expression. The addition of cetuximab to radiation therapy or irinotecan in human tumor xenograft models in mice resulted in an increase in anti-tumor effects compared to radiation therapy or chemotherapy alone.

Cetuximab administered as monotherapy or in combination with concomitant chemotherapy or radiation therapy exhibits nonlinear pharmacokinetics. The area under the concentration time curve (AUC) increased in a greater than dose proportional manner while clearance of cetuximab decreased from 0.08 to 0.02 L/h/m² as the dose increased from 20 to 200 mg/m², and at doses >200 mg/m², it appeared to plateau. The volume of the distribution for cetuximab appeared to be independent of dose and approximated the vascular space of 2–3 L/m².

Following the recommended dose regimen (400 mg/m² initial dose; 250 mg/m² weekly dose), concentrations of cetuximab reached steady-state levels by the third weekly infusion with mean peak and trough concentrations across studies ranging from 168 to 235 and 41 to 85 µg/mL, respectively. The mean half-life of cetuximab was approximately 112 hours (range 63–230 hours). The pharmacokinetics of cetuximab were similar in patients with SCCHN and those with colorectal cancer.

Cetuximab had an approximately 22% (90% confidence interval; 6%, 38%) higher systemic exposure relative to the EU-approved cetuximab used based on a population pharmacokinetic analysis.

Cetuximab is approved in combination with radiation therapy for the initial treatment of locally or regionally advanced squamous cell carcinoma of the head and neck, in combination with platinum-based therapy with 5-FU for the first-line treatment of patients with recurrent locoregional disease or metastatic squamous cell carcinoma of the head and neck or the treatment of patients with recurrent or metastatic squamous cell carcinoma of the head and neck for whom prior platinum-based therapy has failed.

2. RATIONALE, OBJECTIVES, AND BENEFIT - RISK ASSESSMENT

2.1 RATIONALE FOR PERFORMING THE TRIAL

The addition of the monoclonal antibody Cetuximab, which targets the epidermal growth factor receptor (EGFR), to chemotherapy, has improved the response rate, progression-free survival and overall survival for patients with recurrent or metastatic squamous cell cancers of the head and neck (SCCHN) [3]. Cetuximab acts by binding to the extracellular portion of the EGFR molecule and competitively inhibiting the binding of its ligand. However, it does not interfere with ligand-independent EGFR signaling [20].

Although clinically active in a subset of patients, most responders eventually acquire resistance to treatment [21]. Several researchers have published data on molecular mechanisms of acquired resistance to Cetuximab, including dysregulation of EGFR internalization/degradation, alternatively localized EGFR from the cell membrane into the cell's nucleus and strong activation of HER2, HER3 and cMET. Nuclear localized EGFR is highly associated with disease progression, worse overall survival, and enhanced resistance to radiation, chemotherapy, and to anti-EGFR therapies. EGFR up-regulation promotes increased dimerization with HER2 and HER3 leading to their transactivation. Blockade of EGFR and HER2 is shown to lead to loss of HER3 and PI(3)K/Akt dependent signaling.

Afatinib is an oral, irreversible pan-ErbB family tyrosine kinase inhibitor with intracellular activity, which makes it an attractive combinatorial partner to Cetuximab to overcome some of the putative resistance mechanisms described above. A recently published randomized Phase II study has shown that it does not demonstrate cross-resistance with Cetuximab [9].

We hypothesize that the combination of Cetuximab and Afatinib will demonstrate superior clinical efficacy than when used singly or sequentially in the management of advanced SCCHN and propose this single-arm Phase II trial. Tissue arrays will be constructed from where medically feasible tumor biopsies obtained pre-treatment, after 4 weeks on treatment with the combination and again at progression or end of treatment in an attempt to develop predictive biomarkers of response and study mechanisms of inherent or acquired resistance. Multiple high quality immunohistochemical assays will be performed and analyzed with automated image analysis (AQUA, Genoptix®) for EGFR, phospho-EGFR, HER-2, phospho-HER-2, HER-3, HER-4, phospho-Akt, PTEN, cyclin D1, p53 and nuclear proliferating cell nuclear antigen (PCNA).

Results from this exploratory trial will inform future studies with this combination or with other novel targeted therapies in the metastatic setting.

2.2 TRIAL OBJECTIVES**PRIMARY OBJECTIVE**

To determine the response of advanced squamous cell carcinoma of the head and neck region to treatment with a combination of afatinib and cetuximab. Clinical efficacy of the combination treatment will be determined through assessment of response to treatment (tumor shrinkage) based on RECIST v 1.1., duration of response, progression-free survival and overall survival.

SECONDARY OBJECTIVES

To determine impact on long-term efficacy outcomes, safety and tolerability of the combination and laboratory correlates for more effective inhibition of Epidermal Growth Factor Receptor (EGFR) signaling with the combination of Cetuximab and Afatinib. Efficacy outcomes will be assessed by tumor response based on RECIST v 1.1., duration of response, progression-free survival and overall survival. Safety of the combination will be assessed through collection of adverse event (AE) and serious adverse event (SAE) data and monitoring of laboratory tests.

2.3 BENEFIT – RISK ASSESSMENT

For patients with advanced head and neck cancer who have disease progression on a chemotherapy regimen using a platinum compound, there are few salvage therapies that are currently standard of care. We know that the majority of SCCHN tumors overexpress EGFR. Targeting the receptor helps gain disease control in a subset of these patients. Recently, it has been shown that resistance to the EGFR monoclonal antibody (Cetuximab) does not automatically confer cross-resistance to the small molecule inhibitor (Erlotinib) [9]. It therefore seems logical to test a combination of cetuximab and a potent EGFR small molecule inhibitor like afatinib to see if we can improve on response rates and durability of response seen with either agent alone.

Cetuximab and Afatinib combination regimen at the proposed doses has been previously tested in patients with lung cancer who harbor the EGFR mutation and was shown to be safe and effective [22]. We have also built in adequate monitoring measures (periodic physical examinations and laboratory monitoring, AE and SAE reporting) into our trial design to ensure patient safety.

3. DESCRIPTION OF DESIGN AND TRIAL POPULATION

3.1 OVERALL TRIAL DESIGN AND PLAN

Baseline medical history and demographics, prior and concomitant medications, physical exam, weight, height, vital signs, ECOG performance status, laboratory assessments (CBC with differential, CMP, Magnesium levels, pregnancy test for women of reproductive age and coagulation studies (if on anticoagulant therapy), an EKG, CT or MRI of involved disease sites, human papillomavirus (HPV) status (immunohistochemical staining for p16) and a tumor biopsy (where feasible, after progression on previous line of treatment), will be obtained for all patients after they sign the consent form.

Patients will initiate treatment on the afatinib and cetuximab combination regimen. Pre-medication with decadron 10mg, H1 and H2 blockade (at the discretion of the treating facility and physician) may precede the first dose of Cetuximab in week 1 of cycle 1. Premedication with H1 blockade alone may be used beyond the initial dose for patients who do not experience an infusion reaction with the first dose. Oral Afatinib at 30mg daily will start the same day as the Cetuximab. Subsequently, Cetuximab will be dosed at 250mg/m² body surface area, given intravenously weekly (+/- 1 day) or at 500 mg/m² body surface area, given intravenously bi-weekly (+/- 2 days), at the discretion of the treating physician. Each treatment cycle will be 28 days (+/- 3 days) in length.

Alternating Cetuximab dosing schedules from a weekly to bi-weekly dosing schedule, and vice versa, between and within cycles of treatment is permitted per protocol following Sponsor PI discussion and approval.

While on study treatment, patients will be seen weekly (+/- 1 day) or bi-weekly (+/- 2 days) depending on the frequency of cetuximab dosing. During these visits, the following evaluations will be done: adverse event assessment, concomitant medications, physical exam, weight, vital signs and ECOG performance status. Laboratory assessments (CBC with differential, CMP, Magnesium) will be performed prior to cetuximab infusion throughout treatment. Pregnancy test for reproductive age women and coagulation studies if on anticoagulant therapy will be performed every 4 weeks throughout treatment. CT or MRI (at physician discretion) will be performed at the end of cycle 2 (+/- 3 days) and every 2 cycles thereafter (+/- 3 days).

Treatment will be discontinued in the event of \geq grade 3 drug related toxicities that fail to resolve to Grade 2 despite appropriate supportive care or unequivocally progressive disease on clinical exam or surveillance scans. Treatment may also be discontinued for reasons noted in Section 3.3.4, including clinically significant deterioration of the patient's condition, patient noncompliance, investigator determination that it is no longer in the patient's best interest to continue, pregnancy, or withdrawal of consent. Tissue biopsies will be repeated, where

medically feasible, at the end of cycle 1, and at disease progression or end of treatment if discontinued for reasons other than disease progression.

In the situation where patients withdraw consent for treatment on study, we will permit progression and survival data collection unless they specifically withdraw consent for data collection for the trial.

3.2 DISCUSSION OF TRIAL DESIGN

This study will be a single center, single-arm, open-label Phase II trial. The study is expected to enroll 50 patients with advanced squamous cell cancers of the head and neck, who have previously been treated with a platinum-based regimen or with immune checkpoint inhibitor therapy or both. After obtaining consent, patients will undergo a baseline evaluation including tumor assessment (scans performed within 4 weeks of treatment start will be accepted), biopsy (where feasible) and verification of HPV status and then initiate treatment with cetuximab weekly/bi-weekly and oral afatinib daily. Up to a 2-day interval between two 4-week cycles will be permitted. Following the first cycle of treatment, a tumor biopsy will be repeated where medically feasible (for correlative studies), and therapy will be continued. Tumor assessment will be repeated after cycle 2 and every 2 cycles thereafter. Tumor biopsy (for correlative studies) will be repeated again where medically feasible, at disease progression or end of treatment if discontinued for reasons other than disease progression. Results will be compared with historical controls.

3.3 SELECTION OF TRIAL POPULATION

3.3.1 Main diagnosis for study entry

Advanced Squamous Cell Cancers of the Head and Neck Region.

3.3.2 Inclusion criteria

1. Histologically or cytologically confirmed squamous cell carcinoma of the head and neck that is metastatic, recurrent or locally advanced and not treatable with curative intent.
2. Previous treatment with a platinum-based regimen or immune checkpoint inhibitor therapy or both in the R/M (Recurrent/Metastatic) setting. 2-week washout period prior to treatment start will be required.
3. Patients who have experienced progression of disease within 6 months following completion of a platinum-based chemoradiation in the definitive or adjuvant setting will be permitted.

4. Prior cetuximab permitted if it was given as part of multi-modality therapy for initial treatment of locally advanced disease but not for recurrent/metastatic disease.

5. Measurable disease based on RECIST v 1.1. Baseline measurements and evaluations must be obtained within 4 weeks of enrollment. Disease in previously irradiated sites is considered measurable if there has been unequivocal disease progression or biopsy-proven residual carcinoma following radiation therapy.

6. Age ≥ 18 years

7. ECOG performance status ≤ 2

8. Adequate organ function, defined as all of the following:

- Hemoglobin ≥ 8 g/dl.
- Absolute neutrophil count (ANC) ≥ 1000 / mm³.
- Platelet count $\geq 75,000$ / mm³.
- Estimated creatinine clearance > 45 ml / min.
- Total Bilirubin ≤ 1.5 times upper limit of (institutional/central) normal
(Patients with Gilbert's syndrome total bilirubin must be ≤ 4 times institutional upper limit of normal).
- Aspartate amino transferase (AST) or alanine amino transferase (ALT) \leq three times the upper limit of (institutional/central) normal (ULN) (if related to liver metastases \leq five times ULN).

9. Ability to understand and the willingness to sign a written informed consent that is consistent with ICH-GCP guidelines.

10. Negative urine or serum pregnancy test for women of childbearing potential

11. A second eligibility review will always be provided by a Head and Neck Research Team associated for the New Haven Campus and a third review will be provided by the PI.

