3.3.3 Exclusion criteria

1. Prior erlotinib, gefitinib or lapatinib therapy or prior exposure to any investigational EGFR or panErbB reversible or irreversible inhibitor or any prior panitumumab or investigational EGFR-directed monoclonal antibody. Cetuximab is permitted if used for locally advanced disease, as long as no disease progression within 6 months. Cetuximab use is not permitted for recurrent/metastatic disease.

2. Radiotherapy within 2 weeks prior to enrollment. Palliative radiation to target organs may be allowed up to 2 weeks prior to enrollment, as long as there are other target lesions that can be monitored for response to study treatment.
3. Known hypersensitivity to afatinib or its excipients
4. Women of child-bearing potential (WOCBP) and men who are able to father a child, unwilling to be abstinent or use highly effective methods of birth control prior to study entry, for the duration of study participation and for at least 4 weeks after treatment has ended.
5. Pregnant or nursing women.
6. Any history of or concomitant condition that, in the opinion of the Investigator, would compromise the patient's ability to comply with the study or interfere with the evaluation of the efficacy and safety of the test drug.
7. Concomitant malignancies at other sites that are being actively treated with systemic therapy
8. Requiring treatment with any of the prohibited concomitant medications listed in Section 4.2.2.1 that cannot be stopped for the duration of trial participation.
9. Clinically significant interstitial lung disease.
10. Known history of untreated viral hepatitis or HIV.
11. Patients with parenchymal brain metastases are not eligible, unless they have completed local therapy.
12. Leptomeningeal carcinomatosis.

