4.1.4.1.2 Dose reduction for afatinib

Treatment related AEs will be managed by treatment interruptions and subsequent dose reductions of afatinib according to the schedule described in Table 4.1.4.1.2: 1. Given overlapping toxicities, afatinib dose reductions should precede cetuximab dose reductions. Dose reductions will apply to individual patients only. Once the dose has been reduced, it cannot be increased later.

To prevent the development of more severe adverse events, treatment related diarrhea or rash should be managed early and proactively as described in Section 4.2.3.

Table 4.1.4.1.2: 1 Dose reduction scheme for afatinib

AE type and CTCAE Grade	Action	Dose reduction scheme
Events related to study drug: 
 Diarrhea Grade 2 persisting for 2 or more consecutive days (48 hours) despite adequate anti-diarrheal medication/hydration Reduced renal function to \geq Grade 2 as measured by serum creatinine, proteinuria or decrease in glomerular filtration rate of more than 50% from baseline Any other drug related AE Grade \geq3 	Pause treatment until patient has recovered to Grade \leq 2 (Grade \leq 1 for diarrhea or impaired renal function only) or baseline ¹ . Resume treatment at reduced dose according to schedule opposite. If patient has not recovered to Grade \leq 2 (Grade \leq 1 for diarrhea or impaired renal function) or baseline ¹ within 14 days, study treatment	If patient was receiving Afatinib 30 mg daily, resume treatment at a dose of 20 mg daily. If patient was receiving Afatinib 20 mg daily, resume treatment at 20 mg intermittent dosing, 5 days on, 2 days off. If patient was receiving Afatinib 20 mg intermittent dosing, discontinue treatment.

AE type and CTCAE Grade	Action	Dose reduction scheme
	must be permanently discontinued ² .	
Acute onset and/or unexplained worsening of pulmonary systems (dyspnoea, cough, fever)	Pause afatinib while clinical assessment to exclude ILD is completed.	If ILD is ruled out as a cause of symptoms, grade symptoms and relatedness and report as AEs. If AEs are not related, resume afatinib at current dose. If AEs are drug related, follow directions in row above. If ILD is confirmed, discontinue afatinib

¹ Baseline is defined as the CTCAE Grade at the start of treatment

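### As written, inclusion item 8 is met when only one of AST and ALT is within the limit, and no other criterion puts a number on the second enzyme

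*Combined protocol and SAP*

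**What the plan says.** Section 3.3.2, item 8, introduces its list with "Adequate organ function, defined as all of the following". The last bullet opens "Aspartate amino transferase (AST) or alanine amino transferase (ALT" and sets the ceiling at "three times the upper limit of (institutional/central) normal (ULN) (if related to liver metastases", with five times ULN in that case. The synopsis (Main Criteria for Inclusion, item 8) joins the two enzymes with the same word.

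Other text bearing on entry:

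- Section 3.3.2, item 11: "A second eligibility review will always be provided by a Head and Neck Research Team", followed by a third review by the principal investigator.
- Section 3.3.3, exclusion 6: a condition that, in the investigator's opinion, would compromise compliance or "interfere with the evaluation of the efficacy and safety of the test drug".
- Section 3.3.2, item 8, also caps bilirubin, and section 3.3.3, exclusion 10, excludes known untreated viral hepatitis.
- Section 5.3.3: a comprehensive metabolic panel (CMP) is drawn at screening to check eligibility.
- Section 8.1.2: an investigator must document that every inclusion criterion is met.

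**The concern.** A transaminase ceiling at entry is meant to keep out patients with marked liver-enzyme elevation. Joined by *or*, the ceiling binds only the lower of the two values. A hypothetical patient with AST at 2 x ULN and ALT at 12 x ULN meets the bullet as written.

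What is at stake is safety screening and consistent eligibility decisions. Two people applying the same sentence to the same straddling patient could reach opposite answers, each with support in the text. Because section 8.1.2 has eligibility documented against the criteria, this sentence is also what an auditor would check.

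**Working it through.** The plan gives no figure to reproduce, so the check compares the passages and follows their logic.

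**Step 1. How the enzymes combine.** The introduction to item 8 joins the bullets to one another. It does not say how AST and ALT combine inside one bullet. Let L be the applicable limit (3 x ULN, or 5 x ULN if related to liver metastases).

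| AST | ALT | Either enzyme within L (literal) | Each enzyme within L |
|---|---|---|---|
| at or below L | at or below L | met | met |
| at or below L | above L | met | not met |
| above L | at or below L | met | not met |
| above L | above L | not met | not met |

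The two readings differ only in the middle rows, where the values straddle L.

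**Step 2. Does anything else settle it?** The synopsis repeats the same joining word, so it does not. No exclusion in section 3.3.3 gives a transaminase limit. The bilirubin cap and the hepatitis exclusion concern other things. Exclusion 6 is discretionary, and the repeat reviews apply the same sentence. The second enzyme therefore has no numeric cap.

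**Step 3. Does the starting value carry forward into dosing?** Table 4.1.4.1.2: 1 is triggered, for events such as raised transaminases, by "Any other drug related AE Grade" 3 or higher judged related to study drug. Afatinib is paused until recovery to Grade 2 or lower (Grade 1 or lower "for diarrhea or impaired renal function only) or baseline"). The footnote reads "Baseline is defined as the CTCAE Grade at the start of treatment". With B the starting grade, the loosest grade that allows resumption is max(2, B):

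- B of 2 or lower: max(2, B) = 2, so the starting grade changes nothing.
- B = 3: max(2, 3) = 3, so baseline becomes the looser target.

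The starting grade therefore matters only for a patient who begins at Grade 3 or higher and then has a drug-related event that triggers the table. The documents do not print the CTCAE transaminase cut-offs, so the multiple of ULN at which this begins cannot be taken from them.

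**Step 4. The stopping text.** Section 3.1 discontinues treatment when a drug-related toxicity of Grade 3 or higher fails to resolve to Grade 2. Section 3.3.4 lists the same event as a reason for discontinuation. Neither offers return to baseline as an alternative. For B = 3 and recovery to Grade 3 only, the table permits resumption and section 3.1 requires discontinuation. This conflict is not specific to the liver and arises whatever item 8 is taken to mean.

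**The case against.** The strongest reply is that this is a drafting ambiguity. The bullet sits under a heading about adequate organ function, and *or* can be read as applying the limit to whichever transaminase is looked at. Most staff will probably apply the limit to both by habit. The second and third reviews are mandatory, and the criterion still excludes anyone with both enzymes above the limit.

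Much of this stands. It is an ambiguity and not a contradiction, and meeting item 8 is not the same as being enrolled. The whichever-is-measured reading helps less if the screening CMP reports both enzymes. That is an assumption, since the documents do not list the panel's contents. On that assumption both values are on the page, and the text does not say what to do when they disagree.

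Three stronger readings are tempting, and the documents do not support them:

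- A reader might infer that a high starting grade simply becomes the recovery target for afatinib. It is only an alternative to Grade 2 or lower, and sections 3.1 and 3.3.4 do not recognise it.
- A reader might infer that liver toxicity would be hidden in the safety summary. Section 5.3.7.1 collects all adverse events from consent, section 5.3.6.1 grades them by CTCAE, section 5.3.7.3 requires worsening of pre-existing conditions and clinically relevant laboratory changes to be recorded, and section 5.3.3 repeats the CMP before each cetuximab dose. Section 5.3.7.3 does treat pre-existing abnormalities as baseline conditions, but a later rise remains measured and reportable.
- A reader might infer that the rule misclassifies every patient whose enzymes differ. The table in the working shows that it matters only when the values straddle the limit.

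**Conclusion.** The point holds as a minor one. Item 8 and the synopsis, read as written, are satisfied by one in-range transaminase, and nothing else in the plan puts a number on the other. The affected group is limited to patients with straddling values. Its size cannot be derived from the documents and is probably small. The primary ORR test, the power statement and the sample size do not depend on it.

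The conclusion rests on the literal meaning of *or* and on the absence of any other numeric transaminase criterion in the protocol. It does not assume that such a patient would in practice be enrolled.

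The mismatch between the baseline alternative in Table 4.1.4.1.2: 1 and the discontinuation wording in sections 3.1 and 3.3.4 is a separate inconsistency. It needs reconciling, and no view is taken here on which rule is right.

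**What to change.** In section 3.3.2, item 8, and in the synopsis, replace the joining word so that the line reads: *AST and ALT each at or below three times ULN (each at or below five times ULN if related to liver metastases)*. The printed limits stay as they are. If entry on either enzyme alone is really intended, the protocol should say so expressly.

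The cost is a few words in two places. No new test is needed, on the assumption that the CMP already drawn at screening reports both enzymes. A rare patient with straddling values would be screened out.

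As a separate edit, the sponsor should reconcile the recovery wording in Table 4.1.4.1.2: 1 with the discontinuation wording in sections 3.1 and 3.3.4, so that a patient who starts with a high grade is handled the same way under each.
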